7.2 Dose and treatment regimens

Dose reductions for toxicity are permitted for either or both IPs (see Section 6.7).

7.2.1 Cediranib

For all centers, cediranib will be packed in high-density polyethylene bottles with child-resistant closures. The cediranib study treatment will be dispensed to patients. Multiple bottles of study treatment may be required for dispensing in order to make up the desired dose.

Patients will be administered cediranib study treatment tablets orally at a dose of 30 mg od. The planned dose of 30 mg od will be made up of 2 × 15 mg tablets od. One x 20 mg and 1 x 15 mg tablets will be used to manage dose reductions.

Doses of study treatment should be taken at the same time each morning. The dose of cediranib can be taken at the same time as the morning dose of olaparib and can be taken with or without food, in a similar way each morning. For patients with difficulty swallowing tablets, cediranib tablets may be dispersed in non-carbonated drinking water.

If a patient misses a dose, the patient should be advised to take the dose as soon as possible provided this happens within 6 hours of the scheduled time. If it is more than 6 hours after the scheduled time, cediranib should not be taken for that day. Cediranib should be taken as scheduled on the next day. A patient should not take more than a single daily dose on a given day.

7.2.2 Olaparib

For all centers, olaparib will be packed in high-density polyethylene bottles with child-resistant closures. The olaparib study treatment will be dispensed to patients. Multiple bottles of study treatment may be required for dispensing in order to make up the desired dose.

Patients will be administered olaparib study treatment tablets orally at a dose of 200 mg bd. The planned dose of 200 mg bd will be made up of 2 × 100 mg tablets bd. One × 150 mg and 1 × 100 mg tablets will be used to manage dose reductions.

Doses of study treatment should be taken at the same time each day approximately 12 hours apart. All doses should be taken with approximately 240 mL of water. The olaparib treatment tablets should be swallowed whole and not chewed, crushed, dissolved or divided. Olaparib tablets can be taken with or without food.

If vomiting occurs shortly after the study treatment tablets are swallowed, the dose should only be replaced if all of the intact tablets can be seen and counted. Should any patient enrolled on the study miss a scheduled dose for whatever reason (eg., as a result of forgetting to take the tablets or vomiting), the patient will be allowed to take the scheduled dose up to a maximum of 2 hours after that scheduled dose time. If greater than 2 hours after the scheduled dose time, the missed dose is not to be taken and the patient should take their allotted dose at the next scheduled time.

7.3 Labelling

Labels will be prepared in accordance with Good Manufacturing Practice (GMP) and local regulatory guidelines. The labels will fulfil GMP Annex 13 requirements for labelling. Label text will be translated into local language.

Specific dosing instructions will not be included on the label; the site must complete the “Patient Dispensing Card” with the details of the dosing instructions at the time of dispensing. The patient emergency contact details will not be on the label, but can be found in the informed consent and the ‘Patient Dispensing Card’. For emergency purposes, the patient must be in possession of the emergency contact details at all times.

7.4 Storage

All study drugs should be kept in a secure place under appropriate storage conditions. The IP labels on the bottles specify the appropriate storage.

7.5 Compliance

The administration of all study drugs (including IPs) should be recorded in the appropriate sections of the eCRF.

Treatment compliance will be assured by reconciliation of site drug accountability logs. Patients should be given clear instructions on how and when to take their IPs. Patients will self-administer olaparib and cediranib. Study site staff will make tablet counts at regular

intervals during treatment. Compliance will be assessed by the tablet count and the information will be recorded in the appropriate section of the eCRF. After the tablet count has been performed, the remaining tablets will not be returned to the patient but will be retained by the investigative site until reconciliation is completed by the study monitor. All patients must return their bottle(s) of olaparib and cediranib at the appropriate scheduled visit, when a new bottle will be dispensed. Patients will be instructed to record dates of missed or held doses using a handheld electronic device (the same device used for collection of PRO data; see Section 5.3.1). These data will be reviewed by the Investigator at each patient visit and data entered in eCRF by the site staff. Patients must return all containers and any remaining tablets at the end of the study.

7.6 Accountability

The study drug provided for this study will be used only as directed in the study protocol.

The study personnel will account for all study drugs dispensed to and returned from the patient.

Study site personnel, will account for all study drugs received at the site, unused study drugs and for appropriate destruction. Certificates of delivery, destruction and return (as applicable for particular study drug) should be signed.

7.7 Concomitant and other treatments

The Investigator must be informed as soon as possible about any medication taken from the time of screening until the end of the study treatment period (treatment discontinuation or FPV visit). Any concomitant medication(s), including herbal preparations, taken during the study will be recorded in the eCRF.

Medications that should NOT be administered

No other anti-cancer therapy (chemotherapy, immunotherapy, hormonal therapy (Hormone replacement therapy (HRT) is acceptable), RT, biological therapy or other novel agent) is to be permitted while the patient is receiving one or both IPs.

Live virus and bacterial vaccines should not be administered whilst the patient is receiving one or both IPs and during the 30 day follow up period. An increased risk of infection by the administration of live virus and bacterial vaccines has been observed with conventional chemotherapy drugs and the effects with the combination of cediranib and olaparib are unknown.

The use of any natural/herbal products or other “folk remedies” should be discouraged; but use of these products, as well as use of all vitamins, nutritional supplements and all other concomitant medications must be recorded.

Cediranib and inducers of PgP/UGT

In vitro data indicate that cediranib is unlikely to cause interactions with CYP450 inducers, inhibitors, and substrates. Cediranib oxidative metabolism appears to be mediated by flavin-containing monooxygenase enzymes FMO1 and FMO3 and glucuronidation by UGT1A4. Co-administration of cediranib with strong inducers of PgP/UGT decrease cediranib plasma concentrations; therefore, use of potent inducers of UGT/PgP (eg, rifampicin, carbamazepine, phenobarbital, phenytoin and St. John Wort) should be avoided if possible. Cediranib is a substrate of MDR1 (Pgp), and possible substrate of breast cancer resistant protein (BCRP). Cediranib is not an inhibitor of OAT1 and OAT3, but it has a low potential to inhibit MDR1 (Pgp), BCRP, OATP1B1, OATP1B3, OCT2, MATE1. The clinical impact of this finding is unknown. Cediranib may act as an inhibitor of renal tubular MATE2-K, this could increase exposure of co-administered agents such metformin or to endogenous agents such as creatinine; however, the ICON6 study showed that increases of blood creatinine caused by 20 mg/day cediranib treatment were infrequent (4.4%) and only mild in severity, suggesting the clinical impact of renal tubular MATE2-K inhibition by cediranib is small.

Olaparib and CYP 3A4/5 enzymes

CYP3A4/5 are the isozymes predominantly responsible for the metabolic clearance of olaparib. Clinical studies to evaluate the impact of known CYP3A inhibitors and inducers have shown that co-administration of a strong CYP3A inhibitor increased olaparib maximum plasma concentration (C_{max}) 1.42-fold (90% CI: 1.33-1.52) and increased mean area under the plasma drug concentration-time curve (AUC) 2.70-fold (90% CI: 2.44-2.97); co-administration of a strong CYP inducer decreased C_{max} by 71% (treatment ratio: 0.29; 90% CI: 0.24-0.33) and mean AUC by 87% (treatment ratio: 0.13; 90% CI: 0.11-0.16).

Consequently, to ensure patient safety, the following potent inhibitors of CYP3A4/5 must not be used during this study for any patient receiving olaparib (eg, itraconazole, telithromycin, clarithromycin, boosted protease inhibitors, indinavir, saquinavir, nelfinavir, boceprevir, telaprevir) or moderate inhibitors (ciprofloxacin, erythromycin, diltiazem, fluconazole, verapamil) of this isozyme should not be taken with the IPs in this study.

Strong CYP 3A4/5 inducers (eg, phenobarbital, phenytoin, rifampicin, rifabutin, rifapentine, carbamazepine, nevirapine, enzalutamide and St John's Wort) and moderate inducers CYP 3A4 inducers (eg, bosentan, efavirenz, modafinil) should not be taken with the IPs in this study.

After enrollment if the use of any potent inducers or inhibitors of CYP3A4/5 are considered necessary for the patient's safety and welfare, the investigator must contact the AstraZeneca Study Physician. A decision to allow the patient to continue in the study will be made on a case-by-case basis.

Effect of olaparib on other drugs

- CYP3A4 substrates: hormonal contraceptive, simvastatin, cisapride, cyclosporine, ergot alkaloids, fentanyl, pimozide, sirolimus, tacrolimus and quetiapine
- CYP2B6 substrates: bupropion, efavirenz
- OATP1B1 substrates: bosentan, glibenclamide, repaglinide, statins and valsartan
- OCT1, MATE1 and MATE2K substrates: metformin
- OCT2 substrates: serum creatinine
- OAT3 substrates: furosemide, methotrexate

Based on limited in vitro data, olaparib may increase the exposure to substrates of CYP3A4, OATP1B1, OCT1, OCT2, OAT3, MATE1 and MATE2K. Based on limited in vitro data, olaparib may reduce the exposure to substrates of 2B6. Caution should be observed if substrates of these isoenzymes or transporter proteins are co-administered.

Anticoagulant Therapy

Patients who are taking warfarin may participate in this trial; however, it is recommended that prothrombin time (International Normalized Ratio [INR] and activated partial thromboplastin time) be monitored carefully at least once per week for the first month, then monthly if the INR is stable. Subcutaneous heparin and low molecular weight heparin are permitted.

Anti-emetics/Anti-diarrheal

From screening onwards, should a patient develop nausea, vomiting and / or diarrhea, then these symptoms should be reported as AEs (see Section 6.3) and appropriate treatment of the event given.

Palliative radiotherapy

Palliative RT may be used for the treatment of pain at the site of bony metastases that were present at baseline, provided the investigator does not feel that these are indicative of clinical disease progression during the study period. Both IPs should be discontinued for a minimum of 3 days before a patient undergoes therapeutic palliative radiation treatment. Both IPs should be restarted within 4 weeks as long as any bone marrow toxicity has recovered.

Administration of other anti-cancer agents

Patients must not receive any other concurrent anti-cancer therapy, including investigational agents, while on one or both IPs. Patients may continue the use of bisphosphonates or denosumab for bone disease and corticosteroids for the symptomatic control of brain metastases provided the dose is stable before and during the study and they were started at least 4 weeks prior to the first doses of IPs.

Subsequent therapies for cancer

Details of first and subsequent therapies for cancer and/or details of surgery for the treatment of the cancer, after discontinuation of treatment, will be collected until the end of the study.

Other concomitant treatment

Other medication other than that described above, which is considered necessary for the patient's safety and well-being, may be given at the discretion of the Investigator and recorded in the appropriate sections of the eCRF.

In addition, any unplanned diagnostic, therapeutic or surgical procedure performed during the study period must be recorded in the eCRF.

7.8 Post Study Access to Study Treatment

There are no plans to provide olaparib and/or cediranib to the patients after discontinuation of the IPs. After discontinuation of IPs, the investigator will be at liberty to define further most appropriate anti-cancer treatment. Information on subsequent PARP and VEGF inhibitors and other anti-cancer therapies should be recorded on the clinical database as part of survival follow-up.

8. STATISTICAL ANALYSES BY ASTRAZENECA

8.1 Statistical considerations

A comprehensive Statistical Analysis Plan (SAP) will be prepared prior to first patient enrolled and any subsequent amendments will be documented, with final amendments completed prior to database lock. Additional details relating to the ICR will be detailed in the ICR Charter.

An interim futility analysis will take place after 20 evaluable (by Investigator assessment) patients have received at least 1 dose of IP and have been followed for at least 4 months. Patients in the futility analysis will also have their baseline scans reviewed by ICR to evaluate the concordance rate on measurable disease at this stage. Enrollment will continue during the futility analysis. Assuming the study passes the futility assessment, the data cut-off for the primary analysis of ORR will take place 8 months after the last patient has received her first dose of IP, to allow opportunity for all patients to complete at least 4 RECIST follow-up assessments. Patients will be followed for survival and analysis of OS will also take place at this time. Patients should be contacted or other data sources checked (see Section 3.10.2) in the 2 weeks following the data cut-off for the primary analysis to provide current survival data. At this time, the CSR will be written including the analysis of the confirmed ORR by ICR using RECIST 1.1 criteria, supported by Investigator assessment of ORR and by other efficacy endpoints (DoR, DCR, PFS, OS and TDT), PROs and safety/tolerability variables.

Following the data cut-off for the primary analysis, no further statistical analysis of the data will be conducted.

8.2 Sample size estimate

The study originally planned to recruit 100 patients over approximately 12 months. The primary analysis scheduled at 8 months after the last patient received her first dose of IP (approximately 20 months after study start), allows all patients to have at least 4 RECIST follow-up assessments.

An interim futility analysis of ORR (confirmed and/or unconfirmed CRs and PRs based on investigator assessment) will take place after 20 evaluable patients (ie, with measurable disease (by Investigator assessment) have received at least 1 dose of IP and have been followed for at least 4 months. If less than 4 of the 20 have responded the study may be stopped for futility. If 4 or more patients have responded the study will continue to the primary analysis.

The study design was formulated within a Bayesian framework (Fisch et al 2015) based on dual criteria to show improvement over the expected response rate under current standard treatments (20% RR targeted as an improvement over <15% RR based on chemotherapy, Davis et al 2014) and to have a RR of a relevant size (approximately 30%, similar to the RR seen for bevacizumab plus chemotherapy in the AURELIA trial, Pujade-Lauraine et al 2014) defined as follows:

1. to have high confidence (>90%) that the true ORR is at least 20% or probability ($ORR \geq 20\%$) >0.9 and
2. an observed rate of 30/100 is seen at the primary analysis.

The futility rule above (stop if number of responses is <4), was chosen so that the trial may stop if there is a low chance (<10% predictive probability) of 30 or more responses being observed at the primary analysis. Computation of posterior and predictive probabilities used a neutral prior ie, beta (1/3, 1/3) distribution (Kerman 2011), for the ORR. The predictive probability of observing a given number of responses at the end of the trial given the observed responses at the interim analysis is computed using a beta binomial distribution.

With 30 responders out of 100 at the primary analysis we would be >99% confident that the ORR is greater or equal to 20% and 94.6% confident that the ORR is $\geq 23\%$. It is noted that the interim analysis is based on unconfirmed, investigator assessed RECIST data, whereas the primary analysis will be based on ICR assessed data with responses confirmed at least 4 weeks after the initial response. Data from the OCEANS study indicated an approximate 1.5% reduction in response by ICR compared with investigator response (Aghajanian et al 2014). If only 26 patients out of 100 were to meet the latter definition of response at the primary analysis there would still be >90% confidence that the true rate was greater than or equal to 20%.

Assuming median PFS of 6 months, 73% PFS events are expected at the primary analysis at 8 months after the last patient receives her first dose of IP. The original analysis for OS at 12 months after last patient receives her first dose of IP would expect 59% deaths.

The study now plans to recruit approximately 60 patients and analysis of OS, originally planned at 12 months after the last patient received her first dose of IP, will now occur at 8 months after the last patient received her first dose of IP. Based on the revised duration of recruitment and assuming a median PFS of 6 months as originally planned and a median of 12 months for OS, 80% PFS events and 57% OS events are expected to occur at the time of the analysis.

Table 18 presents the 95% CIs for some possible response rates which give an indication of the precision of the response rate that might be seen.

Table 18 Response rates and associated 95% CIs for a sample of 60

Response (n)	Response (%)	95% CI
5	8.3%	(1.3%, 15.3%)
10	16.7%	(7.2%, 26.1%)
15	25.0%	(14.0%, 36.0%)

CI confidence interval

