Assuming the study passes the futility assessment, the data cut-off for the primary analysis of ORR (confirmed CRs + PRs only) will take place 8 months after the last patient has received her first dose of IP, to allow opportunity for all patients to complete at least 4 RECIST follow-up assessments and estimate duration of response (DoR). The primary analysis for the clinical study report (CSR) will be based on the confirmed ORR by ICR using RECIST 1.1 criteria and supported by Investigator assessment of ORR and by other efficacy endpoints (DoR, disease control rate [DCR] and progression free survival [PFS], time to treatment discontinuation or death [TDT]), patient reported outcomes (PROs), and safety and tolerability data. For the primary analysis of ORR by ICR the mean and median of the posterior distribution of ORR will be presented, along with the standard deviation and a 95% credible interval around the mean (based on the highest posterior density [Lee 1997]). ORR by ICR will also be presented with 95% exact (Clopper Pearson) confidence intervals (95% CI).

The posterior probabilities of the ORR being larger than 15%, 20% and 24% will also be computed. To further characterize the response rate, the posterior probability of showing low (<15%), moderate ($\geq 15\%$ - <20%), high ($\geq 20\%$ - <24%) or substantial ($\geq 24\%$) efficacy will be presented.

At the time of primary analysis, ORR and exact 95% CI (Clopper Pearson) will also be presented for the following:

- ORR by investigator assessment
- ORR for both confirmed and unconfirmed responses for ICR assessment
- ORR in the subgroup of patients carrying a somatic deleterious or suspected deleterious mutation in either of the *BRCA* genes (*BRCA1* or *BRCA2*) or in predefined homologous recombination repair (HRR)-associated genes identified with current and potential future tumor based BRCA or HRR gene mutation assays (ICR and Investigator assessment).

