Patients should continue to receive IPs until objective radiological disease progression, unacceptable toxicity or withdrawal of consent. The study originally planned to recruit 100 patients over approximately 12 months. Due to slower than projected recruitment, the study now plans to recruit approximately 60 patients. An interim futility analysis will be undertaken once the first 20 evaluable patients (ie, with measurable disease [by Investigator assessment] and have received at least 1 dose of IP) have been followed for at least 4 months. If fewer than 4 radiological tumor responses are observed at this point, the trial may be considered futile and enrollment stopped. Enrollment will continue whilst the futility analysis is being conducted.

The primary analysis of the study will be based on measurement of ORR in the evaluable for response (EFR) analysis set (CR+PR; confirmed responses only) by Independent Central review (ICR) using RECIST 1.1. The primary analysis will also report analyses of DoR and disease control rate (DCR) by ICR in the EFR analysis set. Other variables analyzed at the primary analysis (ORR, DoR, DCR based on investigator assessment; PFS, overall survival [OS], time to treatment discontinuation or death [TDT], patient-reported outcome [PRO] variables and safety variables) will be summarized using the FAS. The data cut-off for the primary analysis will take place 8 months after the last patient has received her first dose of IP and is the final analysis for the study. This primary data cut-off will be followed by clinical database lock.

[figure not shown]
Patients continuing to receive clinical benefit without meeting any discontinuation criteria during the study, will complete a FPV which will occur at their last scheduled visit prior to the primary data cut-off. Beyond the FPV, patients may continue to receive cediranib and/or olaparib if they are deriving clinical benefit in the opinion of the investigator, and not fulfilling any discontinuation criteria (see Section 4.5).

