8.5.1 Analysis of the primary variable ORR

The primary analysis will be based on ICR assessments of tumor response. Only patients with a confirmed CR or PR, by ICR, at least 4 weeks after the initial response will be counted as responders.

The number of responders (confirmed CR or PR) will be modelled using a binomial distribution with a neutral Beta (1/3,1/3) prior distribution on the rate.

The mean and median of the posterior distribution of ORR will be presented, along with the standard deviation and a 95% credible interval around the mean (based on the highest posterior density [Lee, 1997]). The observed ORR by ICR will also be presented with 95% exact (Clopper Pearson) CIs.

The posterior probabilities of the ORR being larger than 15%, 20% and 24% will be also computed. To further characterize the RR, the posterior probability of showing low (<15%), moderate ($\geq 15\%$ - <20%), high ($\geq 20\%$ - <24%) or substantial ($\geq 24\%$) efficacy will be presented.

Summaries of the number of patients with best response in each of the follow categories will be presented: CR, PR, SD, PD and NE. For the interim analysis, the CR (PR) category will be split into confirmed CR (PR) and unconfirmed CR (PR).

At the time of primary analysis, ORR and exact 95% CI (Clopper Pearson) will be also be presented for the following:

- ORR by investigator assessment
- ORR for both confirmed and unconfirmed responses based on ICR assessment
- ORR based on ICR assessment in the subgroup of patients carrying a somatic deleterious or suspected deleterious variant in either of the *BRCA* genes (*BRCA1* or *BRCA2*) or in HRR-associated genes identified with current and potential future tumor based *BRCA* or HRR gene mutation assays (ICR and Investigator assessment)

The concordance between ORR (confirmed responses) as assessed by ICR and by Investigator will be presented.

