With 30 responders out of 100 at the final analysis we would be >99% confident that the ORR is greater or equal to 20% and 94.6% confident that the ORR is $\geq 23\%$. It is noted that the interim analysis is based on unconfirmed, investigator assessed RECIST data, whereas the final analysis will be based on ICR assessed data with responses confirmed at least 4 weeks after the initial response. Data from the OCEANS study indicated an approximate 1.5% reduction in response by ICR compared with investigator response (Aghajanian et al 2014). If only 26 patients out of 100 were to meet the latter definition of response at the final analysis there would still be >90% confidence that the true rate was greater than or equal to 20%.

Assuming median PFS of 6 months, 73% PFS events are expected at the primary analysis at 8 months after the last patient receives her first dose of IP.

The original analysis for OS at 12 months after last patient receives her first dose of IP would expect 59% deaths.

The study now plans to recruit approximately 60 patients and analysis of OS, originally planned at 12 months after the last patient received her first dose of IP, will now occur at 8 months after the last patient received her first dose of IP. Based on the revised duration of recruitment and assuming a median PFS of 6 months as originally planned and a median of 12 months for OS, 80% PFS events and 57% OS events are expected to occur at the time of the analysis.

Table 1 Response Rates and associated 95% CIs for a sample size of 60

Response (n)	Response (%)	95% CIs
5	8.3%	(1.3%, 15.3%)
10	16.7%	(7.2%, 26.1%)
15	25.0%	(14.0%, 36.0%)

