4.2.7.1 Analysis of the primary efficacy variable ORR

The primary analysis of ORR will be based on ICR assessments of tumor response using the EFR analysis set.

The number of responders (confirmed CR or PR) will be modelled using a binomial distribution with a neutral Beta(1/3,1/3) prior distribution on the rate.

The mean and median of the posterior distribution of ORR will be presented, along with the standard deviation and a 95% credible interval around the mean (based on the highest posterior density [Lee, 1997]). The observed ORR by ICR will also be presented with 95% exact (Clopper Pearson) confidence intervals.

The posterior probabilities of the ORR being larger than 15, 20 and 24% will be also computed. To further characterize the response rate, the posterior probability of showing unacceptable (<15%), low (>15-20%), moderate (>20-24%) or substantial (>24%) efficacy will be presented.

Summaries of the number of patients with best response in each of the follow categories will be presented: CR, PR, SD, PD and Non-Evaluable (NE). The number of patients with an unconfirmed CR or PR will be presented as a sub-category of SD. For the interim analysis the CR (PR) category will be split into confirmed CR (PR) and unconfirmed CR (PR).

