4.2.7.3 Sensitivity analysis

ORR, DCR, DoR and PFS will be re-analyzed at the time of the primary analysis using the investigator assessment of tumor response instead of ICR assessment, as sensitivity analyses.

ORR and exact 95% CI (Clopper Pearson) will be presented for the following:

- ORR by investigator assessment. The numerator (number of confirmed responses) will be based on RECIST as per investigator assessment and the denominator will be based on the full analysis set

- ORR for both confirmed and unconfirmed responses based on ICR assessment. The numerator will include unconfirmed responses in addition to confirmed responses and the denominator will be based on the EFR set.

Sensitivity analyses of PFS, DoR and DCR using the investigators assessment of RECIST will be performed in an analogous manner to those using the ICR described in Section 4.2.7.2 above.

In addition, ORR and BOR using the ICR will be summarised for the FAS.

For patients where measurable disease at baseline is not confirmed by the ICR and who therefore appear in the sensitivity analysis using FAS, but not the primary analysis set (evaluable for response), a detailed description of the reasons for being considered not evaluable will be described in the CSR.

A further comparison of each type of overall objective response (CR, PR, SD, PD, NE or without measurable disease at baseline) between investigator and ICR will be presented using the full analysis set. Details for the patients identified as responders by ICR and not by the investigator, as well as by the investigator and not by ICR will be given.

The concordance between response as assessed by ICR and by investigator with the full analysis set will be summarised by cross-tabulation of the number and percentage of patients with:

- Response declared by investigator and ICR
- Response declared by investigator but not ICR
- Response declared by ICR but not investigator
- No response declared by both investigator and ICR

The overall concordance rate will be calculated as the total number of agreements between investigator and ICR divided by the total sample size.

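### The precision table for ORR at N=60 shows unlabelled Wald intervals, although the confidence interval planned for ORR is exact Clopper-Pearson

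*Protocol*

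**What the plan says.** Protocol version 5.0 cut the sample size from 100 to approximately 60. Section 1.4 gives the reason: "Due to slower than projected recruitment, the study now plans to recruit approximately 60 patients". Section 8.2 then adds Table 18, titled "Response rates and associated 95% CIs for a sample of 60", with the sentence "Table 18 presents the 95% CIs for some possible response rates which give an indication of the precision of the response rate". The table has three rows:

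| Responders | Rate | Stated 95% CI |
|---|---|---|
| 5/60 | 8.3% | (1.3%, 15.3%) |
| 10/60 | 16.7% | (7.2%, 26.1%) |
| 15/60 | 25.0% | (14.0%, 36.0%) |

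SAP section 1.3 carries the same rows and limits in Table 1, "Response Rates and associated 95% CIs for a sample size of 60". Neither table, nor the text around it, names the interval method.

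The analysis sections do name one. For the primary variable, protocol section 8.5.1 says "The observed ORR by ICR will also be presented with 95% exact (Clopper Pearson) CIs" and SAP section 4.2.7.1 says "The observed ORR by ICR will also be presented with 95% exact (Clopper Pearson) confidence intervals". The Statistical methods part of the protocol synopsis agrees. For the supportive ORR analyses, SAP section 4.2.7.3 says "ORR and exact 95% CI (Clopper Pearson) will be presented for the following". The one other interval planned for ORR is a 95% highest-posterior-density (HPD) credible interval under a Beta(1/3, 1/3) prior (protocol section 8.5.1, SAP section 4.2.7.1). No Wald interval for ORR is planned in either document.

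**The concern.** A precision table in a sample-size section should preview the interval the trial will report. This one does so neither for the Clopper-Pearson CI nor for the HPD interval, and with no method label the reader cannot tell. Someone who later sees 10/60 reported with an exact interval of 8.3% to 28.5% will find 7.2% to 26.1% in the protocol with no explanation of the gap.

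The table also carries more weight than its size suggests. The dual criteria and the posterior confidence statements in section 8.2 are still expressed per 100 patients, so these three rows are the only statement of ORR precision at the sample size now planned.

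**Working it through.** **Inputs.** n = 60 and x = 5, 10, 15 (protocol Table 18, SAP Table 1); two-sided 95%, z = 1.96; prior Beta(1/3, 1/3) (protocol section 8.5.1).

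**Step 1: reproduce the stated figures.** The Wald interval is p ± 1.96·√(p(1−p)/60).

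- 5/60: p = 0.0833, SE = 0.03568, half-width 0.0699, giving (1.34%, 15.33%).
- 10/60: p = 0.1667, SE = 0.04811, half-width 0.0943, giving (7.24%, 26.10%).
- 15/60: p = 0.25, SE = 0.05590, half-width 0.1096, giving (14.04%, 35.96%).

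All six round to the printed limits. Clopper-Pearson, Wilson, Agresti-Coull, Jeffreys, continuity-corrected Wald, Wald with n−1, and the HPD and equal-tailed intervals from the Beta(1/3, 1/3) posterior were also tried. None of them reproduces the whole table.

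**Step 2: the planned confidence interval.** For Clopper-Pearson, the lower limit is the 2.5% quantile of Beta(x, n−x+1) and the upper limit is the 97.5% quantile of Beta(x+1, n−x).

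**Step 3: the planned credible interval.** This is the shortest interval holding 95% of Beta(x+1/3, 60−x+1/3).

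| x/60 | Stated (Wald) | Clopper-Pearson | HPD |
|---|---|---|---|
| 5 | (1.3%, 15.3%) | (2.8%, 18.4%) | (2.5%, 15.9%) |
| 10 | (7.2%, 26.1%) | (8.3%, 28.5%) | (8.1%, 26.5%) |
| 15 | (14.0%, 36.0%) | (14.7%, 37.9%) | (14.8%, 36.2%) |

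**Step 4: differences in percentage points, from unrounded limits.**

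| x/60 | Lower, CP − Wald | Upper, CP − Wald | Width: Wald | Width: CP | Width: HPD |
|---|---|---|---|---|---|
| 5 | 2.76 − 1.34 = 1.4 | 18.39 − 15.33 = 3.1 | 14.0 | 15.6 | 13.5 |
| 10 | 8.29 − 7.24 = 1.1 | 28.52 − 26.10 = 2.4 | 18.9 | 20.2 | 18.4 |
| 15 | 14.72 − 14.04 = 0.7 | 37.86 − 35.96 = 1.9 | 21.9 | 23.1 | 21.5 |

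The Wald intervals are therefore 1.2 to 1.6 points narrower than the planned CIs. Relative to the HPD intervals they are about half a point wider, and sit lower: by 0.7 to 1.1 points at the lower limit and 0.3 to 0.6 at the upper.

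**Step 5: coverage.** Summing binomial probabilities over x = 0 to 60 at the three tabulated rates, the Wald interval covers 87.6%, 93.2% and 93.9%, and Clopper-Pearson covers 98.5%, 96.3% and 96.3%. The first row is the weakest as a nominal 95% interval.

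**The case against.** The table is illustrative. It promises only an indication of precision, for an approximate sample size, and does not claim to use the analysis method. The arithmetic is right for a Wald interval, so no sentence in either document is contradicted. Nothing depends on it: N=60 follows from recruitment, and neither the futility rule nor the posterior thresholds of 15%, 20% and 24% use it. Moving to Clopper-Pearson takes no limit in these three rows across any of those thresholds.

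The primary summary is also Bayesian, with the exact CI presented alongside. Against the HPD interval the table is slightly too wide, so it does not overstate precision on that measure. Finally, the primary denominator is the evaluable-for-response set, which may be smaller than 60, so exact agreement with the report was never assured. On this view a normal-approximation label would be enough.

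These points hold as limits on the importance of the finding: it is a mismatch of method and a missing label, with no calculation slip and no consequence for the design. They do not make the table consistent with the plan. It matches neither planned interval, and a label alone would leave it displaying an interval the trial does not intend to report.

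**Conclusion.** The point holds. All six limits in both tables are Wald, and all six differ at the printed precision from the exact Clopper-Pearson limits planned for ORR. The largest gap is at 5/60, where the stated upper limit is 15.3% and the planned method gives 18.4%. Relative to Clopper-Pearson the table is conservative at the lower end, understates the upper end, and overstates precision by 1.2 to 1.6 points of width.

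The correction is modest in size and should be made; the design, the futility rule and the analysis are unaffected. The replacement limits take the denominator as exactly 60, as the tables do. The documents give no expected size for the evaluable-for-response set; at the same response rate, a smaller set would give wider intervals.

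**What to change.** In protocol Table 18 and SAP Table 1, replace the limits with 5/60 (2.8%, 18.4%), 10/60 (8.3%, 28.5%) and 15/60 (14.7%, 37.9%), and state in the heading or a footnote that these are exact Clopper-Pearson 95% CIs. Rows nearer the roughly 30% response rate that section 8.2 calls relevant are optional: 17/60 gives (17.5%, 41.4%) and 18/60 gives (18.8%, 43.2%).

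The cost is six numbers and one label in each document, with no change to design or analysis. The stated confidence intervals become 1.2 to 1.6 points wider.
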